#### Carriage cohort

The cohort will include all mother–newborn dyads/triads who meet the following criteria:

- Selected to be in the carriage cohort
- Included in the primary analysis cohort
- Contributed swabs at day 0 and day 6 (but not necessarily at day 28 or 4 months)
- All members of the dyad/triad alive and participating in the study at the time of the 4–month visit

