#### Carriage cohort (500 mothers and their children –250 pairs per country)

1. *S. pneumoniae* in infant nasopharyngeal swabs
2. *Klebsiella* in infant nasopharyngeal swabs
3. *E. coli* in infant rectal swabs
4. *Klebsiella* in infant rectal swabs
5. *Pseudomonas* in infant rectal swabs
6. *S. aureus* in infant oropharyngeal swabs

7. GBS in infant oropharyngeal swabs
8. GAS in infant oropharyngeal swabs
9. *S. aureus* in breast milk samples
10. GBS in breast milk samples
11. GAS in breast milk samples
12. *E. coli* in breast milk samples
13. *Pseudomonas* in breast milk samples
14. *Klebsiella* in breast milk samples
15. *E. coli* in NPS collected from women
16. *S. pneumoniae* in NPS collected from women
17. *Klebsiella* in NPS collected from women
18. *S. aureus* in OPS collected from women
19. GBS in OPS collected from women
20. GAS in OPS collected from women
21. Resistance to AZI, oxacillin and amoxicillin among isolates of *S. aureus*
22. Resistance to AZI, oxacillin and amoxicillin among isolates of GBS
23. Resistance to AZI, oxacillin and amoxicillin among isolates of GAS
24. Resistance to AZI, oxacillin and amoxicillin among isolates of *S. pneumoniae*
25. Resistance to AZI, oxacillin and amoxicillin among isolates of *Klebsiella*

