### 4.4 Study Variables

(ICH E3; 9.5.1. ICH E9; 2.2.2)

The study activities for all mother–newborn dyads/triads enrolled in the study are summarised in the table below (Table 1). In the subset enrolled in the carriage sub–study (n=250 per country), additional home visits were conducted at day 6 and 4 months, and in the subset enrolled in the anthropometrical sub–study (n=1,000 per country) additional home visits were conducted at 6 and 12 months. Surveillance for deaths, sepsis and adverse events was up to day 28 for all participants. In addition, for participants in the carriage sub–study, surveillance for deaths and serious adverse events extended to 4 months, and for participants in the anthropometric sub–study surveillance extended to 12 months.

Note that day 0 is the date of birth rather than date of randomisation as in the study protocol. We have chosen to re–define follow up time as time from birth rather than time from randomisation to ensure that the definition of neonatal sepsis—one of the components of the primary outcome—is consistent with the standard definition.

**Table 1** Summary of study activities

	Pregnancy	Day 0  or Day -1 or Day 1	Day 28 (±4days)
Sensitisation & consent	X		
Health facility visit for delivery		X	
Review of inclusion & exclusion criteria		X	
Randomisation & treatment		X	
Discharge review		X	
Active follow–up (home visit)			X
Passive surveillance 		—————→	

Day 0 is defined to be the day of birth. Note that randomisation and discharge might not occur on the same day as the delivery.

Passive surveillance for adverse events, mortality and sepsis. The surveillance period extends to 4 months for mothers and children participating in the carriage sub–study and to 12 months for children participating in the anthropometrical sub–study.

**Table 2** Carriage samples collected from mother–newborn pairs (n=500; 250/country) enrolled in the carriage sub–study

	Day 0  (or Day –1)	Day 6 (±2 days)	Day 28 (±4 days)	4 Months (±2 weeks)
Mother				
Recto–Vaginal	X 			
Nasopharyngeal	X 	X		
Oropharyngeal	X 	X		
Breast milk		X	X	X
Newborn				
Nasopharyngeal	X 	X	X	X
Oropharyngeal	X 	X	X	X
Rectal	X 	X	X	X

Samples collected on the day of birth (baby) or randomisation (mother) were collected at the health facility. Note that randomisation often occurred the day before delivery.  

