#### Primary analysis cohort

The cohort will include all mother–newborn dyads (or triads in the case of twins) who have been randomised to one of the study arms and where the day–28 survival status is known for all members of the dyad/triad. Dyads/triads where the survival status of all members cannot be determined from the day 28 visit or previous death records, or who have withdrawn from the study, will be excluded from the cohort.

We do not anticipate significant non–compliance and therefore do not intend to conduct a per protocol analysis. In the unlikely event that >10% of the study women do not ingest the study pills then we will conduct an additional analysis of the primary outcome restricted to mother–newborn dyads/triads where the mother is known to have ingested the medication.

Each subject’s inclusion or exclusion status in the primary analysis population will be assigned prior to breaking the code.

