### Carriage and Anthropometric cohorts

Since outcomes are actively recorded in these cohorts, missing data may be recorded for some of the outcomes analysed in the Carriage and Anthropometric cohorts.

We anticipate some missing data at the 4-month time point because of the interruption due to the COVID-19 pandemic. Therefore, an available case analysis will be conducted in the Carriage cohort. The occurrence of missing data is unlikely to be associated with any particular characteristic of the women/neonates, and the risk of bias due to missing data is small.

The anthropometric cohort was recruited prior to the COVID-19 pandemic. Nevertheless, we expect some missing data due to loss to follow up, and will therefore conduct an available case analysis in this cohort. We will assess the risk of selection bias by comparing the baseline characteristics of children who are lost to follow up with those who remain in the cohort throughout follow up.

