## 7 Summary of Study Data

See dummy tables and consort diagram.

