## **8.2 Carriage cohort**

### **Maternal carriage**

Maternal bacterial carriage will be analysed by estimating the proportion of women positive at day 6 and the proportion positive at one or more of the post-intervention time points (i.e. day 6, day 28 or 4 months). The latter will be estimated using women who have data available at all time points, i.e. women missing day 28 or 4-month data will be excluded from this analysis. However, a secondary analysis will be done using a multiply imputed dataset in which missing day 28 and 4-month carriage data are imputed using day 0 and day 6 data. For bacteria that are isolated from multiple sample types an individual will be identified as positive if bacteria are isolated from any of the samples (Table 5). For example,

women will be considered positive for *Klebsiella* at day 6 if bacteria are isolated from either the NPS or breast milk sample. Besides presenting the prevalence of individual bacteria, the bacteria will be grouped into gram positives (*S. pneumoniae*, *S. aureus*, GBS, GAS) and gram negatives (*E. coli*, *pseudomonas*, *Klebsiella*).

We will use logistic regression to compare the proportion positive by study arm adjusting for carriage at day 0. For example, *S. aureus* carriage on day 6 will be compared by calculating an odds ratio adjusted for *S. aureus* carriage on day 0. If the prevalence of a carriage outcome is <4% then an unadjusted odds ratio will be presented instead of the adjusted OR and Fisher's exact test will be used to calculate the p-value. The cut-off of 4% has been chosen to ensure that logistic regression is not used when there are fewer than 10 events per parameter as recommended by Peduzzi et al (1996).

A longitudinal analysis of carriage will be conducted using data from breast milk samples collected on day 6, day 28 and at 4 months. As with the other analyses, logistic regression will be used to adjust for carriage at day 0 where possible (i.e. provided the prevalence is  $\geq 4\%$ ). Two versions of the analysis will be done: the first will be restricted to women with complete data at all three time points, and the second will be done using the multiply imputed dataset. The prevalence at each time point and in each arm will be displayed graphically.

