## 9 Safety Analyses

We will report the numbers of severe adverse, hospitalisations and deaths in mothers and neonates in the Primary cohort and number of deaths in the Carriage and Anthropometric cohorts. When calculating the incidence, each subject will be counted only once and any repetitions will be ignored; the denominator will be the total population size. P-values will be calculated using Fisher's exact test.

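### The Carriage cohort admits only dyads/triads alive and participating at 4 months, so its planned death count is essentially zero by construction and valid earlier swabs are discarded

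*SAP*

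**What the plan says.** Section 6.2 (Carriage cohort) sets four entry conditions: selection for the cohort, membership of the Primary analysis cohort, swabs at day 0 and day 6 (later swabs are expressly not required), and "All members of the dyad/triad alive and participating in the study at the time of the 4–month visit".

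Section 9 plans to report the "number of deaths in the Carriage and Anthropometric cohorts", with the total population size as denominator and p-values from Fisher's exact test. Section 4.4 states that for the carriage sub-study "surveillance for deaths and serious adverse events extended to 4 months".

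Section 8.2 compares arms at day 6 and over all post-intervention time points for mothers, and at day 0, day 6, day 28 and 4 months for infants.

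Three other places bear on the point:

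- Section 3.4 uses the cohort name more loosely, for "500 mothers and their children".
- Section 6.2 (Primary analysis cohort) removes dyads/triads with unknown day-28 survival status "or who have withdrawn from the study, will be excluded from the cohort".
- Section 7 says only "See dummy tables and consort diagram"; those tables are not part of the document at hand.

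**The concern.** An analysis set defined by survival to a given time cannot be used to count deaths up to that time. A row of 0 v 0 with p = 1 could be read as a safety result, when the deaths were taken out by definition. The deaths from day 29 to 4 months, which the sub-study was set up to detect, would go uncounted by arm for anyone not covered by another cohort.

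The rule also conditions the day 0, day 6 and day 28 carriage comparisons on something that happens after those swabs were taken and after randomisation. One member's death after the day-6 swab, or one member's loss after day 28, removes every swab of the dyad or triad. In a triad, the death of one twin removes the mother and the surviving twin. The earlier comparisons need no knowledge of 4-month status.

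**Working it through.** **Deaths: the sections side by side**

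1. Entry to the cohort requires all members to be alive at the 4-month visit (6.2).
2. Death surveillance for carriage participants ends at 4 months (4.4).
3. Deaths are counted in that cohort (9).

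From 1 and 2, a death under surveillance can fall inside the cohort only if it follows a visit held early in the ±2-week window (Table 2), or if it occurs after 4 months in an infant who is also in the anthropometric sub-study. Otherwise the count is zero. The Anthropometric cohort does not have this problem: it requires survival only to day 28, and its surveillance runs to 12 months.

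**What the zero row would show.** The SAP gives 250 pairs per country; assume also about 250 per arm.

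- Fisher's exact test, 0/250 v 0/250: p = 1.
- Two-sided 95% upper limit for 0/250: 1 − 0.025^(1/250) = 1.46%. Printed beside the zero, it would look like evidence of low mortality, but it has no meaning because the zero is imposed.

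**Deaths that would be expected among 500 newborns**

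- To day 28, at the 0.7% observed mortality in section 5: 0.007 × 500 = 3.5. The chance of none is (1 − 0.007)^500 ≈ 0.03. These deaths are still reported in the Primary cohort.
- Day 29 to 4 months: the SAP gives no rate. At an assumed 0.2–0.7%: 0.002 × 500 = 1.0 to 0.007 × 500 = 3.5. The chance of at least one is 1 − exp(−1.0) = 63% to 1 − exp(−3.5) = 97%. The number going unreported is lower where the infant is also in the anthropometric sub-study.

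**Swabs discarded.** The SAP does not say how many stop participating after day 28. Assume 1–3%.

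| Quantity | At 1% | At 3% |
|---|---|---|
| Dyads removed (share × 500) | 5 | 15 |
| Day-6 samples, six per pair in Table 2 | up to 30 | up to 90 |
| Day-28 samples, four per pair in Table 2 | up to 20 | up to 60 |
| Standard error ratio, √(1/(1 − share)) | 1.005 | 1.015 |

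**Possible bias.** The shift in the risk difference is the excluded share times the carriage gap between excluded and retained dyads. If the gap exists in one arm only and is an assumed 10–20 percentage points: 0.01 × 0.10 = 0.1 points to 0.03 × 0.20 = 0.6 points.

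**The case against.** The strongest reply is that section 9 may mean everyone selected for the sub-study. The first entry condition in section 6.2 already uses the cohort name in that sense, since it would otherwise be circular, and section 3.4 does the same. The total-population denominator in section 9 fits that reading, and section 4.4 describes surveillance of sub-study participants rather than of an analysis set. On that reading the zero disappears and only an unnamed denominator remains. The reading is possible, but section 9 does not state it, and 6.2 is where the populations are formally defined.

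Second, the Primary cohort's withdrawal clause has no time limit. Read literally, it may already exclude formal withdrawals after day 28, and the 4-month condition would then add only later deaths and other losses. This stands as a caution: 5–15 dyads may overstate what the 4-month condition alone removes.

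Third, the effects are small. With 250 per arm, Fisher's test gives p = 0.061 for 5 v 0 deaths and 0.030 for 6 v 0, so a corrected row would seldom show a difference. That is true, but a count of deaths by arm is worth reporting without a significant test.

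Fourth, a cohort alive to 4 months avoids imputing carriage after death. That aim is sound, but it can be met without discarding swabs taken while the participant was alive.

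**Conclusion.** The concern holds. Followed as written, the SAP produces a death comparison in the Carriage cohort that is essentially empty by definition, and it drops valid earlier swabs for a reason unrelated to the comparisons that use them.

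The contradiction on deaths rests on the text alone. The sizes do not: mortality from day 29 to 4 months, loss after day 28, the carriage gap and the 250 per arm are all assumptions. On those assumptions the loss of precision and the bias in carriage are small. The clearer harm is to safety reporting: for carriage mothers and carriage-only infants, the SAP text provides no by-arm count of deaths from day 29 to 4 months. The dummy tables might provide one but could not be checked. The primary endpoint and the listed 28-day maternal endpoints are unaffected. The point should be corrected before the analysis.

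**What to change.** - **Section 9:** report deaths by arm from birth to 4 months, mothers and infants separately, in all dyads/triads selected for the carriage sub-study, and name that denominator. Deleting the 4-month condition would not be enough on its own, because the day-6 swab requirement still excludes anyone who dies before that swab.
- **Section 6.2, Carriage cohort:** delete the 4-month alive-and-participating condition and analyse each time point in those with a swab at that time.
- **Section 6.2, Primary analysis cohort:** state that withdrawal means withdrawal by day 28. Dyads/triads excluded under that rule stay excluded.
- **Section 8.2:** impute only visits at which the participant was alive. For positivity at one or more time points, classify a participant who died on the swabs taken while alive.
- **Sections 6.4 and 8.2:** as a separate tidy-up, reconcile the missing-data wording. Section 6.4 says "Therefore, an available case analysis will be conducted in the Carriage cohort", while for the any-time-point maternal outcome section 8.2 says "women missing day 28 or 4-month data will be excluded from this analysis" and adds multiple imputation as a second analysis; infant carriage is handled in a similar way.

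The cost is SAP wording only, with no new data. Denominators will differ slightly between time points, and participants who died will contribute fewer visits to the any-time-point outcome.

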## 4 Study Methods

### 4.1 General Study Design and Plan

(ICH E3; 9)

PregnAnZI-2 was a phase III, double-blinded, placebo-controlled randomized clinical trial in which women in labour were randomized to either a single 2g dose of oral AZI or placebo. The study recruited 12,000 women (6750 in The Gambia and 5250 in Burkina Faso).

In The Gambia, women were recruited in two health facilities—Bundung Maternal and Child Health Hospital and Serrekunda Health Centre. In Burkina Faso, recruitment took place in a number of health facilities in Nanoro and Yako health districts.

Women were consented during the antenatal care visits but the study number (randomisation number) was only assigned after screening during labour, provided the woman met the necessary inclusion and exclusion criteria for participation.

Before March 23rd 2020, women and their newborns were visited at 28 day (either at home or at the health facility). After March 23rd 2020, women were not visited at home because of the risk of SARS-CoV-2 transmission, instead the day 28 interview was conducted by telephone. Cases of maternal and neonatal sepsis were identified through passive case detection at the study health facilities during the 28-day follow up period.

Additional scheduled visits at 6 and 12 months were performed for the first 2,000 women recruited (half in The Gambia and half in Burkina Faso) to assess infant anthropometrical measurements, hospitalization and all-cause mortality.

Carriage samples (recto-vaginal swabs, NPS, OPS, rectal swabs and breast milk samples) were collected from 500 randomly selected mother-newborn dyads (or triads in the case of twins). The samples were collected at day 0, day 6, day 28 and at 4 months.

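### The Carriage cohort's 4-month criterion discards valid earlier swabs from dyads with a death by 4 months, or a withdrawal or true loss after day 28, and keeps those dyads out of the imputation

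*SAP*

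**What the plan says.** SAP section 6.2, Carriage cohort, lists four cumulative criteria.

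1. The dyad or triad was selected for the sub-study.
2. "Included in the primary analysis cohort". That cohort (6.2, Primary analysis cohort) leaves out dyads whose day-28 survival status is unknown for any member, and dyads that have withdrawn. The withdrawal clause carries no date.
3. "Contributed swabs at day 0 and day 6 (but not necessarily at day 28 or 4 months").
4. Every member must be "alive and participating in the study at the time of the" 4-month visit.

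Section 4.1 says that the samples "were collected from 500 randomly selected mother-newborn dyads" (250 per country in section 4.4).

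Section 8.2 compares maternal carriage at day 6 and at any later visit, and infant carriage at day 0, day 6, day 28 and 4 months. Resistance is analysed in the same way. For both mothers and infants, missing day-28 and 4-month results are imputed from day 0 and day 6. For mothers, "a secondary analysis will be done using a multiply imputed dataset in which missing day 28 and 4-month carriage data are imputed" from those samples.

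Section 6.4 states: "We anticipate some missing data at the 4-month time point because of the interruption" due to the pandemic. It answers this with an available-case analysis.

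**The concern.** The third criterion keeps a dyad whose later swabs are missing. The fourth removes it, with all its earlier swabs, if any one member is no longer alive and participating at 4 months. A day-6 comparison is then made in a group selected on something that happened months after randomisation and after the swab was taken.

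This works against the rest of the plan. Available-case analysis and imputation are the SAP's two answers to missing later swabs, and both run inside a cohort from which the true drop-outs have already been removed. The Anthropometric cohort in the same section is treated differently: it requires infants to be alive and participating only at day 28, although follow-up runs to 12 months, and 6.4 compares those lost with those retained. The Carriage cohort is conditioned on its last visit and has no such comparison.

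At stake are the precision of the carriage and resistance comparisons and, under some conditions, their freedom from bias. All are secondary endpoints. The primary endpoint is not touched.

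**Working it through.** **Step 1: which dyads does the fourth criterion alone remove?** Take dyads with day-0 and day-6 swabs and apply the criteria to each event.

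| Event | Primary cohort (criterion 2) | 4-month status (criterion 4) | Result |
|---|---|---|---|
| 4-month visit missed, still enrolled | met | can be met | stays; missing swab can be imputed |
| Withdrawal or unknown survival status by day 28 | fails | not needed | out whatever criterion 4 says |
| Truly lost between day 28 and 4 months | met | fails | out because of criterion 4 |
| Withdrawal between day 28 and 4 months | unclear, as the clause is undated | fails | out because of criterion 4, possibly also criterion 2 |
| Death of a member after the day-6 swabs and by 4 months | met, since survival status is known | fails | out because of criterion 4 |

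The criterion therefore accounts for deaths up to 4 months and for withdrawals and true losses after day 28. A death before day 6 will generally fail the third criterion anyway.

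**Step 2: the one stated figure that depends on cohort size.** The 4% prevalence cut-off in 8.2 is meant to secure 10 events per parameter. With two parameters (study arm and day-0 carriage) this is 0.04 × 500 / 2 = 10.0. It reproduces, but only with all 500 dyads.

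**Step 3: precision.** The SAP gives no attrition figure for the carriage sub-study. The 8% in section 5 is the sample-size allowance for the main trial. I assume 5-15%. With prevalence and allocation held fixed, the standard error is proportional to 1/√N, so its ratio is 1/√(1 − d).

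| Assumed loss d | Dyads removed of 500 | SE ratio | Events per parameter at 4% |
|---|---|---|---|
| 5% | 25 | 1/√0.95 = 1.026 | 0.04 × 475 / 2 = 9.5 |
| 8% | 40 | 1/√0.92 = 1.043 | 0.04 × 460 / 2 = 9.2 |
| 15% | 75 | 1/√0.85 = 1.0847 | 0.04 × 425 / 2 = 8.5 |

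Standard errors rise by about 3-8%. The counts are upper limits, because some of the 500 will fail the first three criteria anyway. For the same reason, the shortfall below 10 events per parameter is not due to the fourth criterion alone.

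**Step 4: when would there be bias?** All inputs here are assumed. Let true day-6 prevalence be 20% in both arms, so that the true odds ratio (azithromycin against control) is 1.00. Prevalence among those retained is (0.20 − d × p)/(1 − d), where p is prevalence among leavers.

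- 8% leave each arm and leavers carry at 20%: retained prevalence is 20% in both arms, odds ratio 1.00.
- 8% leave each arm; control leavers carry at 30%, azithromycin leavers at 20%. Control (0.20 − 0.024)/0.92 = 0.191; azithromycin (0.20 − 0.016)/0.92 = 0.200; odds ratio 1.06.
- 15% leave control and 8% leave azithromycin; leavers carry at 40% in both arms. Control (0.20 − 0.060)/0.85 = 0.165; azithromycin (0.20 − 0.032)/0.92 = 0.183; odds ratio 1.13.

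Bias needs leaving to be related to carriage and arm. Without that, only precision is lost.

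**The case against.** The strongest reply is that the loss the SAP expects is already handled. The pandemic interruption is described as missing data, the third criterion tolerates missing later swabs, and the fourth asks for participation, not for a completed visit. That stands. A reader might infer from 6.4 that dyads missed because of COVID-19 are thrown out, but the text does not say so. Participation is undefined, and a dyad still enrolled can remain and be imputed. What the reply cannot rescue is a dyad that withdrew, has a death, or cannot be traced and so cannot be shown to be participating.

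Secondly, losses between day 6 and day 28 should not be charged to this criterion, because the primary cohort already excludes them. That also stands, apart from deaths, which the primary cohort keeps.

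Thirdly, the trial is double-blind, and 6.4 judges missing data unlikely to be related to participant characteristics. A reader might infer that the day-6 results are biased. The documents give no evidence of that. The judgement in 6.4, however, follows directly on the pandemic interruption and says nothing specific about deaths or voluntary withdrawal.

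Finally, deleting the fourth criterion might seem enough. It may not be: read literally, the undated withdrawal clause still excludes a mother who withdrew at 3 months, and the deletion leaves open how deaths are treated.

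**Conclusion.** The point holds in a limited form. The fourth criterion removes valid earlier swabs because of a later event, and keeps those dyads out of both methods meant to deal with missing later results. It applies to deaths up to 4 months and to withdrawals and true losses after day 28, and not to visits merely missed.

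The certain consequence is some loss of precision: at most 25-75 of 500 dyads and about 3-8% on the standard error, if 5-15% were lost in this way. That range is an assumption and does not come from the SAP. Bias is possible but not shown, and neither its size nor its direction can be determined from the document. The consequences are modest, but the change should be made because the swabs have already been collected and the correction costs little.

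**What to change.** In section 6.2, Carriage cohort:

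- Delete the fourth criterion.
- Define the analysis set at each time point by the swabs available at that visit, together with the maternal day-0 swab where the model adjusts for it.
- State that the primary cohort's withdrawal exclusion does not remove carriage swabs collected before a withdrawal.

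In section 8.2:

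- Include dyads that left alive after day 6 in the multiple imputation for mothers and infants.
- Keep swabs taken before a death in the comparisons for those visits, do not impute carriage after death, and say how deaths enter the any-time-point outcome.
- Make clear that the complete-data version of the infant analyses means complete for the comparison in hand. If it means complete at every visit, infants who left would still be missing from the day-0 and day-6 comparisons in that version.
- Show denominators by visit and arm.

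The cost is a few sentences in two sections and denominators that vary by visit. No new data are needed.
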